18.0 Health Information and Privacy Compliance

18.1 Select which of the following is applicable to your research:

My research does not require access to individual health information and therefore assert HIPAA does not apply.

I am requesting that all research participants sign a HIPCO approved HIPAA Disclosure Authorization to participate in the research (either the standalone form or the combined consent and HIPAA Authorization).

I am requesting the IRB to approve a Waiver or an alteration of research participant authorization to participate in the research.

Appropriate Use for Research:

An external IRB (e.g. Advarra) is reviewing and we are requesting use of the authorization language embedded in the template consent form in lieu of the U of M stand-alone HIPAA Authorization. Note: External IRB must be serving as the privacy board for this option.

18.2 Identify the source of Private Health Information you will be using for your research (Check all that apply)

I will use the Informatics Consulting Services (ICS) available through CTSI (also referred to as the University's Information Exchange (IE) or data shelter) to pull records for me

I will collect information directly from research participants.

I will use University services to access and retrieve records from the Bone Marrow Transplant (BMPT) database, also known as the HSCT (Hematopoietic Stem Cell Transplant) database.

I will pull records directly from EPIC.

I will retrieve record directly from axiUm / MiPACS

I will receive data from the Center for Medicare/Medicaid Services

I will receive a limited data set from another institution

Other. Describe:

18.3 Explain how you will ensure that only records of patients who have agreed to have their information used for research will be reviewed. N/A

In an AHC-IS supported desktop or laptop.

Provide UMN device numbers of all devices:

Store Analyze Share

Other.

Indicate if data will be collected, downloaded, accessed, shared or stored using a server, desktop, laptop, external drive or mobile device (including a tablet computer such as an iPad or a smartform (iPhone or Android devices) that you have not already identified in the preceding questions

I will use a server not previously listed to collect/download research data

I will use a desktop or laptop not previously listed

I will use an external hard drive or USB drive ("flash" or "thumb" drives) not previously listed

I will use a mobile device such as an tablet or smartphone not previously listed

18.7 Consultants. Vendors. Third Parties.

John Hopkins University will have responsibility for data analysis. Additionally, Production Transcripts is a professional transcription service that will be used to transcribe audio recordings of qualitative interviews. Audio recordings will be securely uploaded to their secure website and the transcripts will be securely shared with the research team once completed.

18.8 Links to identifiable data:

Individualized links are generated via Qualtrics and saved on the server. Links are destroyed at the end of data collection.

18.9 Sharing of Data with Research Team Members.

Data will be shared via Box, Qualtrics and the secure server. See 19.1 "Data Security".

18.10 Storage of Documents:

All electronic data will be maintained on a University of Minnesota secure server folder and a Box folder. Paper forms of the data will be located in a locked file cabinet in [name] ([name] research office) only accessible to the research team. The office containing the files is also locked. Unless the data are being filed or accessed, these cabinets will remain locked.

18.11 Disposal of Documents:

Per University of Minnesota and the School of Public Health security guidelines, participant data will be maintained on the secure project folder for approximately 2-3 years which is the time anticipated it will take to disseminate any and all research papers or presentations from these data. Baseline, follow-up, or disposition surveys inputted into Qualtrics databases that contained a participant's identifier (name)

SOCIAL PROTOCOL (HRP-580)

PROTOCOL TITLE: The Residential Care Transition Module

VERSION DATE: 2/10/2022

for tracking will be de-identified upon study completion. De-identified records will be kept indefinitely, in order to encourage data sharing submitted to the National Institute on Aging.

19.0 Confidentiality

19.1 Data Security:

Who Will Manage the Study Data

[name] (the PI), [name] (the administrative supplement PI), the TCs, the research coordinators, and graduate research assistants will have primary responsibility for managing all study data. Research assistants who work under the supervision of [name] in the Families and LTC Projects at the University of Minnesota may also enter, clean, and assist the PI and other RCTM team members to manage data as appropriate during the course of the project.

[name] team uses VPN and Remote Desktop Connection to access study data. They are not to download, view, or save any project-related data on their personal laptops or any mobile data storage device. Staff working remotely will continue use of these secure environments as needed. Note: University staff calling from personal lines outside of the University will block their personal numbers when able, and note they are calling from a personal line and request a callback to a work-based telephone number, or alternatively use a google voice account.

Confidentiality Assurance and Data Management

Names and contact information are included in study tracking documents for the purposes of interview reminders and completion of the various data collection procedures. However, data used for analysis will be de-identified according to standard procedures. Procedures for data collection and storage are described above.

As mentioned above, baseline, follow-up, or disposition surveys inputted into Qualtrics databases that contained a participant's identifier (name) for tracking will be de-identified upon study completion. De-identified records will be kept indefinitely, in order to encourage data sharing submitted to the National Institute on Aging.

20.0 Provisions to Monitor the Data to Ensure the Safety of Participants

20.1 Data Integrity Monitoring.

[name] (the PI) and the research coordinators will have primary responsibility for managing all study data. Research assistants who work under the supervision of [name] in the Families and LTC Projects at the University of Minnesota may also enter, clean, and assist the PI and research coordinators manage data as appropriate during the course of the project.

Prior to University of Minnesota Institutional Review Board (IRB) submission, [name] will identify a Data Monitoring Officer (DMO) at the University of Minnesota. The DMO will be a senior faculty member with experience conducting clinical trials.

SOCIAL PROTOCOL (HRP-580)

PROTOCOL TITLE: The Residential Care Transition Module

VERSION DATE: 2/10/2022

Review process. [name] and the DMO will review data monitoring and safety activities annually during the 5-year project period. The responsibility of [name] (who also has oversight for the data management and analysis of the project) will include the production of an administrative report that will highlight study accrual. In addition, [name] will provide information on any deviations from the approved protocol (e.g., deviations in adhering to study eligibility criteria), error rates, and any other issues related to the progress of the study. The DMO will review the administrative report to ensure ongoing quality control, and will work with [name] if necessary to identify individual cases to ascertain any deviations in the approved study protocol. Following this review, the administrative report will be presented to the National Institute on Aging (NIA). In instances of adverse events (see Data Safety Monitoring Plan), the DMO, the NIA project officer, and the University of Minnesota IRB will be notified per below specifications.

The administrative reports will include the following:

1. Table of contents
2. Narrative/trial summary
 - a. Summary of main findings
 - b. Discussion of issues or problems
 - c. Report preparation procedures
3. Study description
 - a. Project organizational chart, personnel
 - b. Brief statement of purpose of trial
 - c. Projected timetable and schedule
4. Study administration
 - a. Recruitment and participant status
 - i. Table 1: Enrollment by year or month of study
 - ii. Figure 1: Comparison of target to actual enrollment by month
 - b. Forms status
 - i. Status of forms (e.g., consent, completing of screener, baseline assessment battery, etc.)

Data Report.

[name] will also prepare interim analysis reports for review with the DMO. These interim analysis reports will include the following:

1. Recruitment and participant status
 - a. Table 2: Targeted/Planned Enrollment Table
 - b. Table 3: Demographic and key baseline characteristics by group
2. Safety assessment for all participants
 - a. Table 4: Treatment duration for all participants
 - b. Table 5: Adverse events by participant
 - c. Table 6: Serious adverse events by participant
 - d. Table 7: Participant deaths
 - e. Table 8: Participants without capacity to consent during follow-up

Reports from the DMO (largely taken from National Institute of Allergy and Infectious Diseases guidelines).

SOCIAL PROTOCOL (HRP-580)

PROTOCOL TITLE: The Residential Care Transition Module

VERSION DATE: 2/10/2022

At the conclusion of each annual review, the DMO will discuss her/his recommendations and findings with [name]. If necessary, the DMO will also issue a written summary report that identifies key issues in the administrative, safety, and data reports and provides overall safety assessment and recommendations. Any rationale for recommendations will be included where appropriate. The report will not include confidential information. Following dissemination of this report to [name], [name] will provide the report to NIA and the Co-Investigators for review.

The DMO will notify [name] of any findings of a serious nature or recommendations to discontinue all or part of the intervention. [name] will then immediately inform the project officer at NIA of this recommendation.

20.2 Data Safety Monitoring.

A data monitoring safety plan (DMSP) that includes a data safety and monitoring officer is proposed to provide additional oversight of the research protocol and adverse event reporting, if necessary.

The main activities of the DMSP will be as follows (taken from National Institute of Allergy and Infectious Diseases guidelines):

1. Review of interim and cumulative data for any evidence of study-related adverse events (AEs);
2. Review of interim/cumulative data for evidence of efficacy of the intervention;
3. Review of data quality, completeness, and timeliness;
4. Review the adequacy of compliance with goals for recruitment and retention, including those related to the participation of women and minorities;
5. Review adherence to the protocol;
6. Review factors that might affect the study outcome or compromise the confidentiality of the data (such as protocol violations, unmasking, etc.); and
7. Identification of factors external to the study such as scientific or therapeutic developments that may impact participant safety or the ethics of the study.

Safety reports. In addition to producing administrative reports on an annual basis to the DMO, [name] will generate annual safety reports that will list adverse events, serious events, unexpected events, events related to or associated with the intervention, and the potential causality of the intervention to the event for each participant. If the research team becomes aware of an adverse event or unanticipated problem occurring while a participant is enrolled in the study (from consent through the participant's final data collection), the event will be documented and/or reported per the protocol below. Events will be documented/reported as adverse events per the protocol if they meet one of the following criteria: a participant alerts study staff of a new or worsening health problem that causes the participant to 1) be unable to perform their daily routine, 2) seek medical care (provider visit, hospitalization, residential care placement, etc.), or 3) take a new medication. Conditions existing prior to study enrollment that have not worsened/changed will not be considered adverse events and will not be documented/reported. Per the University of Minnesota IRB guidelines, all events or information that indicates a new or increased risk, or a safety issue, will be promptly reported.

SOCIAL PROTOCOL (HRP-580)

PROTOCOL TITLE: The Residential Care Transition Module

VERSION DATE: 2/10/2022

Taken from earlier National Institutes of Mental Health policy on Data and Safety Monitoring in Clinical Trials, the definition of each event is as follows:

Adverse event. Any untoward medical occurrence in a patient or clinical investigation participant which does not necessarily have to have a causal relationship with the treatment. An adverse event can therefore be any unfavorable and unintended sign (including an abnormal laboratory finding, for example), symptom, or disease temporally associated with the participants' involvement in research, whether or not considered related to participation in the research.

Serious adverse event. Any adverse experience that results in any of the following outcomes: death, a life threatening experience, inpatient hospitalization, a persistent or significant disability/incapacity, or a congenital anomaly/birth defect. Important medical events that may not result in death, be life threatening, or require hospitalization may be considered a serious adverse experience when based upon appropriate medical judgment, and they may require medical or surgical intervention to prevent one of the outcomes listed in this definition.

Unexpected. Any adverse experience, the specificity or severity of which is not consistent with the risk information described in the [protocol or consent documents].

Related to (or associated with) the intervention. There is a reasonable possibility that the experience may have been caused by the intervention.

Causality. A reasonable possibility that the product is etiologically related to the adverse event. Causality assessment includes, for example, assessment of temporal relationships, dechallenge/rechallenge information, association with (or lack of association with) underlying disease, presence (or absence) of a more likely cause, plausibility, etc.

Survey responses regarding health information will not be considered adverse events, unless otherwise communicated to the study staff. [Note: Medical events or emergencies of a non-participant will not be considered/document as adverse events]. Regardless of the classification of an event (adverse event versus serious adverse event), only those events determined to be potentially related to the participant's involvement in research will be reported to IRB promptly. All other adverse events reported to study staff by participants will be recorded and reported annually via routine reports. Any participant deaths will also be promptly reported, regardless of the cause.

In the instance of an adverse event, [name] and/or the study team will classify whether the event is unexpected, adverse, or seriously adverse, whether the event is unexpected or related to the intervention, and what potentially caused the event. Per the protocol, [name] will review the data routinely and will alert both the DMO as well as NIA as needed if these events occur.

All AEs (following consent) will be collected on an adverse event form, in electronic format. AEs experienced by a participant during a study procedure (i.e. intervention/survey) and are considered potentially related to the participant's involvement in research will be reported within 5 days of discovery to the University of Minnesota IRB (per the University's IRB procedures) and annually to the NIA, DMO, and IRB in data monitoring reports.

AEs that occur outside of the context of a study procedure (i.e. intervention/survey), as well as those that are determined to be not related to the participant's involvement in the study, will be

SOCIAL PROTOCOL (HRP-580)

PROTOCOL TITLE: The Residential Care Transition Module

VERSION DATE: 2/10/2022

documented via the team's electronic AE form and included in the annual report (to be shared with IRB, DMO, and NIA Program Officer).

SAEs that are unanticipated and related to the intervention will be reported to the IRB, NIA Program Officer, and to the DMO within 48 hours of our team's knowledge of SAE. The summary of all other SAEs (i.e. those determined not related to study involvement) will be included in the annual report (to be shared with IRB, DMO, and NIA Program Officer).

Deaths determined not-related to the study will be reported to the IRB within 5 days of the team's knowledge of the participant's death, and reported to the Safety Officer and NIA Program Officer via routine annual reports. Though unlikely, if a participant's death during the project enrollment has a possible relationship to the study, it will be reported in expedited fashion (within 24 hours of the team's knowledge of a participant's death) to the University of Minnesota IRB, the NIA Program Officer, and to the DMO. A written SAE report will be submitted soon thereafter.

No adverse events are expected to be related to study involvement. However, due to the nature of our study population, possible adverse events (i.e. general medical events and/or emergencies) may occur during the time a participant is enrolled in the study. These events will be documented and/or reported according to the protocol.

[name] will present the safety report to the DMO to ensure that there are no negative effects of the treatment. The DMO will review the safety reports annually to ensure that the proper procedure was followed and to identify any potential trends in the data. [name] will present the safety reports to NIA if adverse events occur.

Relationships between the Proposed Data Monitoring and Safety Plan and the IRB

We will notify the University of Minnesota IRB of our data monitoring and safety plan. If the University of Minnesota IRB requests it, we will provide feedback to the IRB of these data monitoring activities on an annual basis (in addition to the annual progress reported required by the University of Minnesota IRB). A brief summary report will be sent to the IRB documenting that a review of the data took place on a given date and will outline the DMO's review of any adverse or unanticipated events. Any requests for modification in the protocol will also be forwarded to the University of Minnesota's IRB.

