14.0 Risks to Participants

14.1 Foreseeable Risks:

Since the study involves no invasive procedures, there will be no physical risks to study participants. The consideration of need is potentially stressful, and thus there are possible psychological risks for the caregiver. However, the research team has considerable experience providing psychosocial support to dementia caregivers on various protocols and serious psychological risks are unlikely to occur based on this experience. The potential social or legal risks for the participants relate only to possible violations of confidentiality. Given the procedures outlined below, such risks are highly unlikely.

The experience of the research team and the exclusion of caregivers with serious psychiatric illness will minimize the possibility of psychological risks. The unlikelihood of such problems is evident from the absence of any clinically significant problems during the past 13 years that the research team has operated various protocols related to dementia caregiving intervention research. The research coordinator and research assistant will be trained to interview in ways that are non-threatening, friendly, and respectful. We will emphasize to all participants that they do not have to complete any question they do not want to answer, and that the interview may be terminated at any time according to their wishes. We will stress to ADRD caregivers that their decision to discontinue the study will in no way affect the services they are receiving from the University of Minnesota, long-term care facility, or other entities.

In the event a caregiver does become upset during the interview process, the research coordinator or research assistant will contact [name], who will be available for consultation. If a caregiver is in crisis because of their care situation or some other reason, research staff will be instructed to consult with [name]. With the caregiver's permission, we will then contact the appropriate resource person in an external agency (e.g., the Alzheimer's Association). Based on the research team's experience working with their caregiving families, we expect very few or no such instances to occur. If a member of the research team does identify neglect or other potentially inappropriate care practices, Adult Protective Services will be notified to protect the rights of persons with dementia and their families.

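### The adverse-event criteria record caregiver distress only when it has reported functional or medical consequences, so other Section 14.1 escalations have no specified route to the safety report

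*Combined protocol and SAP*

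**What the plan says.** Section 14.1 (Foreseeable Risks) says that "there will be no physical risks to study participants" and that "The potential social or legal risks for the participants relate only to possible violations of confidentiality". It also says: "The consideration of need is potentially stressful, and thus there are possible psychological risks for the caregiver". Two responses follow. "In the event a caregiver does become upset during the interview process, the research coordinator or research assistant will contact" a designated person, who is available for consultation. "If a caregiver is in crisis because of their care situation or some other reason, research staff will be instructed to consult" a designated person, after which an outside agency may be contacted if the caregiver agrees. Neither response mentions an adverse-event form, a log or the Data Monitoring Officer (DMO).

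Section 20.2 (Safety reports) sets the recording rule. An event is documented when a participant alerts staff to "a new or worsening health problem that causes the participant to 1) be unable to perform their daily routine, 2) seek medical care", or start a new medication. The formal definition that follows is much wider: it takes in unwelcome signs and symptoms of any kind that coincide with taking part, whatever their cause. Survey answers about health do not count unless staff learn of the problem in some other way.

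The safety report goes to the DMO "to ensure that there are no negative effects of the treatment". The safety tables listed in Section 20.1 (Data Report, Tables 4 to 8) cover treatment duration, adverse events, serious adverse events, deaths and loss of capacity to consent.

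**The concern.** The recording rule fits poorly with the risk that the protocol itself foresees. The rule is written around illness that interrupts routine, leads to care or leads to medication, and Section 20.2 says that the events it anticipates are ordinary medical ones. The foreseen risk is emotional, and its handling sits in another section with no link to safety recording.

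Two things are at stake. First, an absence of distress events in the DMO's tables would be hard to interpret: it could mean that no escalation occurred, or that escalations occurred and did not meet the criteria. Second, with narrow criteria beside a wide definition, two staff members could classify the same event differently, each with support from the text.

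**Working it through.** The protocol states no figure on this point, so the check is to run the plausible cases through the texts.

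| Case | Section 14.1 response | Three recording criteria | General definition | Stated route to DMO tables |
|---|---|---|---|---|
| Upset in a survey interview, consultation held, settles | Yes | Not met | Wide enough to include it | None |
| Crisis, outside agency contacted, routine kept, no care or new medication | Yes | Not met | Wide enough to include it | None |
| Distress that the participant reports has stopped the daily routine | Possibly | Met | Included | Yes |
| Distress that the participant reports has led to a provider visit or new medication | Possibly | Met | Included | Yes |
| Worse distress shown only in survey answers | Not triggered by the answers alone | Not met | Arguable | None; survey answers are set aside |

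The gap is the first two rows: an escalation under Section 14.1 without a reported functional or medical consequence.

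Other provisions in the plan might close it:

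- **Prompt-reporting rule (Section 20.2).** It covers information pointing to a new or greater risk, or to a safety issue. Distress already foreseen in Section 14.1 is not clearly a new risk. A crisis might count as a safety issue, but the sentence refers to IRB guidelines and names no DMO route.
- **Five-day IRB rule for events during a session or survey (Section 20.2).** It applies to adverse events, so the event must first count as one.
- **DMO review of accumulating data (Section 20.2).** Outcome review is framed as efficacy. Section 17.1 describes interim analyses as not applicable, and Tables 2 to 8 hold no outcome data.

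None of these gives the first two rows a specified route.

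Contact differs by arm, which matters for any tabulation. The inputs are 120 per arm and six RCTM sessions (Sections 1.1 and 4.1), quarterly counselor calls to all participants and three follow-up surveys (Section 5.3), and about 12 months of participation (Section 8.1). I assume one call per quarter and full delivery.

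- Calls per participant: 12 / 3 = 4 in both arms.
- Counselor contacts per participant: RCTM 6 + 4 = 10; control 4. Ratio 10 / 4 = 2.5.
- Per arm: 10 × 120 = 1,200 against 4 × 120 = 480. The difference is the 6 × 120 = 720 scheduled sessions.
- If all three follow-up surveys were done by telephone: (10 + 3) / (4 + 3) = 13 / 7 = 1.86.

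If the chance of an escalation per contact were identical in both arms, raw counts would still be about 1.9 to 2.5 times as high in the RCTM arm, before ad hoc counseling is counted.

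**The case against.** The strongest reply is that the criteria refer to a health problem without limiting it to physical health, so distress with real consequences is recorded and reaches the DMO. That is correct. A reader might infer from the mismatch that the criteria exclude distress altogether, or that the DMO's review is blind to it. The documents do not support that: the third and fourth rows of the table are captured, and the prompt-reporting rule may reach a crisis.

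Psychological harm is also observed elsewhere. Depressive symptoms and subjective stress are compared by arm over 12 months (Section 17.1). The counselor logs the content of sessions (Section 5.3, Treatment fidelity) and of control calls (Section 5.2, Usual Care). Reasons for withdrawal are sought (Section 13.2). The post-evaluation interviews ask whether sessions made strain better or worse (Section 5.3). These would help to detect sustained worsening in the final analysis, but none is specified as an input to the safety tables.

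It can also be said that requiring a functional or medical consequence is a reasonable threshold in a study judged to be of minimal risk (Section 22.6), where passing emotion is expected in counseling. That holds for ordinary emotion. It is weaker for events that staff themselves judged to need consultation or outside contact.

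Finally, a reader might multiply the 720 planned sessions by some escalation rate to estimate missed events. The documents give no rate, and Section 14.1 expects few such cases, if any. Its clause on upset concerns interviews rather than counseling sessions, and its crisis clause covers crises of any origin. No such estimate is supportable.

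**Conclusion.** The point holds in a limited form. The recording criteria capture psychological distress, the main foreseen participant risk apart from confidentiality, only when the participant reports that it stopped the daily routine, led to medical care or led to a new medication. Other escalations under Section 14.1 have no specified route to the adverse-event form or the DMO tables, although the section's own definition could include them and the stated purpose of the report calls for them.

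The size is a defined class of events, not a count. The number may be very small, but a low number reassures only if the events would have been recorded. The conclusion assumes that the public text is complete on this point; an adverse-event form or staff manual that already captures escalations would settle it.

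**What to change.** Reconcile Section 14.1 with the recording criteria and the general definition in Section 20.2:

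1. Add as a recording criterion any upset or crisis that triggers the Section 14.1 consultation or outside contact. State that ordinary transient emotion in counseling does not count.
2. List these events in the DMO report by arm and by setting (counseling session, quarterly call, survey interview), with the number of contacts of each kind as denominator.
3. Note beside the table that the RCTM arm has more contact and so more opportunity for distress to be observed; raw counts by arm should not be read as evidence of harm.

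The handling of distress is unchanged. The cost is new wording on the adverse-event form, one report table and a few more entries, with no new staff or participant procedure. The by-arm comparison still needs care even with denominators, because sessions and brief calls differ in content and length. As this version is dated 2/10/2022, much of the contact may already have taken place. The counselor's session and call logs may allow some retrospective tabulation, but they were not designed to record escalations and may be incomplete.
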